8.4.5 National recruitment success

8.4.5.1 Enrollment rates per month and year across regions with centralized and local recruitment strategies

Descriptive statistics will be used to describe enrollment rates including enrollment per month based on age, sex, gender, ethnicity, and region (rural/vs urban), and what means of recruitment (existing cohort/clinic, postcards, ads, earned media) were used. We will also analyze utility of postcards (how many signed up for study as a function of postcards sent) and response rate based on age, sex, gender, ethnicity, rural/vs urban.

8.4.5.2 Screen fail rate and reasons

Descriptive statistics will be used to describe total screen fail rate and reasons and by age, sex, gender, ethnicity and region.

8.4.5.3 Projected enrollment rates vs actual enrollment rates

Descriptive statistics will be used to compare projected enrollment rates versus actual enrollment rates. Information will be presented in the form of a projected enrollment graph and actual enrollment graph showing levels of enrollment as various recruitment strategies were deployed.

8.4.6 Change in levels of physical activity and sleep quality, as measured by:

a. Actigraphy

Ambulatory actigraphy will be assessed as a measure of total daily physical activity and sleep fragmentation and whether their modification lessens the risk of cognitive decline. The degree of sleep fragmentation will be quantified for each participant using the metric kRA, a novel metric that was developed based on modelling actigraphic data as a series of state transitions between rest and activity, and quantifying the transition probabilities¹¹. The triaxial actigraphy data, sampled at 50-60Hz, are used to compute activity counts within each 15 second epoch using a published approach, and arousal is indicated by a non-zero activity count within an epoch, after a sustained period of zero counts. Higher kRA indicates greater sleep fragmentation. In addition, we will quantify total daily physical activity.

b. EEG wearable devices

Sleep stages will be extracted from the overnight EEG data using the manufacturer's algorithms, and will be compared pre- and post-BHSP to quantify effects of the BHSP intervention on sleep architecture. We will compute standard metrics of sleep architecture including total sleep time, sleep efficiency, and wake time after sleep onset, as well as proportion of time spent in each of wake, stage N1, stage N2, stage N3, and REM sleep.

c. Cardiopulmonary sensors (ANNE devices)

For participants in the optional cardiopulmonary sensor sub-study, we will quantify the apnea hypopnea index (AHI), oxygen desaturation index (ODI), hypoxemia burden, and time with oxygen saturation below 90% (O2<90). A participant will be considered to have sleep apnea if their AHI is greater than or equal to 15. In addition, we will quantify 24-hour resting heart rate, and average heart rate, which are important physiological consequences of sleep apnea.

Baseline levels of physical activity, sleep fragmentation, slow wave sleep, and indices of sleep apnea and resting heart rate will be compared with those found after receiving 12 months of engagement with the BHSP using the MMRM approach, adjusting for covariates such as age, sex and education. In addition, an interaction effect of these

measures and time will be assessed while burst cognitive testing scores are used as the dependent variable and physical activity, sleep fragmentation, slow wave, sleep, and indices of sleep apnea and resting heart rate are categorized according to their quantiles.

8.4.7 Saliva sample collection, to characterize the distribution of age adjusted polygenic hazard scores (PHS) within the BHSP study group.

The PHS model developed by Desikan¹² will be used to derive age-specific risk estimates for the development of Alzheimer's Disease within the CTU BHSP cohort.

Methodology:

To accomplish this exploratory outcome, the Desikan PHS model will be employed, which is based on the Cox proportional hazards assumption, to calculate risk scores for Alzheimer's disease (AD) using individual genetic profiles from the CTU BHSP cohort. The logarithm of hazards associated with 31 SNPs identified by Desikan, along with APOE variant status, is incorporated into the risk score calculation using the standard equation for Polygenic Risk Score (PRS) calculation (Equation 1). This process generates a risk score for each individual based on their genetic profile.

Analyses:

To validate the predictive value of our risk scores, we will initially examine the distribution of scores within three phenotypic classes: Cognitively Unimpaired (CU), Subjective Cognitive Impairment (SCI), and Mild Cognitive Impairment (MCI). We will also assess the distribution of risk scores between Affected (MCI) and Control (CU, SCI) groups. We will also evaluate the predictive value of the risk scores by incorporating them into a Generalized Linear Model, aiming to distinguish the Affected condition from the Control group.

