9.3.1 Actigraphy

Physical activity and sleep monitoring using actigraphy (Axivity AX3) will be assessed at Baseline and Month 12. The Axivity is an accelerometer used to detect movement, vibrations, and orientation changes. The Axivity device will be mailed to participants. After study equipment and materials are shipped to and received by the participant, study staff will instruct the participant on the proper application and use of the Axivity over remote video-conference. The participant will be given an instruction card containing contact information of study staff should they have any questions. The participant will be shown how to place the device on their non-dominant wrist by study staff, and participants will be instructed to wear the devices continuously for 14 days, even when bathing or swimming. During the 14 days, participants will be asked to track their work and sleep hours in a diary. At the end of 14 days, participants will return the device to SRI using a pre-paid, pre-addressed package. This procedure will be repeated at the Month 12 remote visit.

9.3.2 *EEG Recording*

Overnight EEG recording will be assessed at Baseline and Month 12 using the MUSE S Headband (Interaxon Inc, Toronto, Ontario, Canada). The MUSE S Headband is a commercially-available consumer headband that has 5 sensors, 2 on the forehead, 2 behind the ears, plus 1 reference sensors, to detect and measure EEG signals. The EEG headband and iPod with Muse app installed will be mailed to participants. After study equipment and materials are shipped to and received by the participant, study staff will instruct the participant on the proper application and use of the Muse over remote video-conference. Participants will use the iPod with the Muse app to capture EEG sleep recordings. Study coordinators will use a pseudo email and password, which will be linked to a central study e-mail address (provided by the sleep team at SRI) to initially sign-up for the app prior to mailing the study iPod to participants. Recordings will be linked to the associated Muse headband device number only and will not include any PHI.

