 - i. Levels of engagement (i.e. percent of chapters completed), ratings of satisfaction, and dropout rates from the intervention
 - ii. Levels of engagement in the program as a function of individual characteristics and risk profile
 - iii. Levels of engagement as a moderator of within person change in outcomes.
 - iv. Association between change in modifiable risk factors and change in cognition
- D.** To develop a successful comprehensive national recruitment plan to fully enroll the PTC with engagement stakeholder groups including participants, citizen advisors, and community partners

3 Power and Sample Size Determination

Sample size/power calculation was done based on effect size for one-group pre-/post-design. According to Becker, the effect size ¹ for such a design should be defined as, assuming the standard deviation (SD) at pre- and post-test are equal,

$$ES = \frac{\text{mean change}}{\text{SD baseline}} = \frac{\text{mean change}}{\text{SD change} / \sqrt{2(1 - r)}}$$

where r is correlation between pre- and post-scores. Note that

$$\text{var}(\text{mean change}) = 2\text{var}(\text{baseline})(1 - r)$$

Sample size can then be determined based on the following test statistic

$$T = \frac{\text{mean change}}{\text{SD change}/\sqrt{n}} = \frac{\text{ES}}{\sqrt{2(1-r)/n}}$$

i.e., the corresponding sample size formula for 80% power at 5% significance level to detect ES is given by

$$n = \frac{(1.96 + 0.84)^2}{(\text{mean change}/\text{SD change})^2} + 2 = \frac{(1.96 + 0.84)^2}{\text{ES}^2/[2(1-r)]} + 2$$

Note that plus 2 ($\approx 2 \times 1.96^2$) is to approximate Z-test with sample size for t-test².

Therefore, the sample sizes for detecting small and moderate magnitudes of ES³ at 2-sided 5% significance level with 80% power are given below for values of correlation r

ES	r	n
0.2 (small)	0.2	316
	0.3	277
	0.4	238
	0.5	198
0.5 (medium)	0.2	53
	0.3	46
	0.4	40
	0.5	34

4 Samples of Interest

- a. **Enrolled Sample:** Includes all participants who consented to screening.
- b. **Intention To Treat (ITT) Sample:** Includes all participants who (1) meet screening criteria (2) and completed at least 1 assessment at baseline.
- c. **Modified Intention to Treat (mITT) Sample:** Includes all eligible participants who (1) have completed at least one assessment for the outcome of interest and (2) registered for BHP.

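### SAP 8.4.6 asks whether modifying device-measured activity and sleep lessens cognitive decline, but its quantile-by-time test cannot separate modification from level

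*SAP*

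**What the plan says.** SAP 8.4.6 introduces actigraphy as covering "physical activity and sleep fragmentation and whether their modification lessens the risk of cognitive decline". Its closing paragraph then gives two analyses.

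1. A pre-post comparison. "Baseline levels of physical activity, sleep fragmentation, slow wave sleep" and related indices are compared with Month 12 values by MMRM, "adjusting for covariates such as age, sex and education". Cognition is not in this model.
2. An interaction model. These "measures and time will be assessed while burst cognitive testing scores are used as the dependent variable", and the device measures "are categorized according to their quantiles". The visit that supplies the quantile is not named. No change score is specified, and no covariates are listed for this model.

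The EEG paragraph of the same section says sleep stages will be "compared pre- and post-BHSP to quantify effects of the BHSP intervention on sleep architecture".

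Protocol 9.3.1 states: "Physical activity and sleep monitoring using actigraphy (Axivity AX3) will be assessed at Baseline and Month 12". Protocol 9.3.2 gives the same two time points for EEG, so a within-person change in each device measure is available. Burst testing runs at five time points (Protocol 10.1.6).

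SAP 8.4.4.5 does model longitudinal change in behaviour against cognitive performance, but takes the behaviour from the lifestyle questionnaires, not from the devices.

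**The concern.** The question is about modification: if a person's activity rises or sleep becomes less fragmented over the year, does that person's cognition hold up better? The interaction asks something else, namely whether people in different quantiles of activity or sleep have different cognitive slopes. That is a contrast between people, and it carries health status and natural course with it.

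Two errors could follow. A significant interaction could be read as support for modification when no one's modification was tested. A real link between device-measured change and cognitive change could also be missed or blurred. Neither depends on the loss of information from cutting at quantiles. Both would remain with continuous levels.

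**Working it through.** **Step 1: the plan's own figures.** No power figure is given for 8.4.6. The only one is Table 1 of Protocol 13.1, for the primary outcome, from n = (1.96 + 0.84)² × 2(1 − r)/ES² + 2. For ES 0.2 and r 0.3 this is 7.84 × 1.4/0.04 + 2 = 276.4, rounded up to the stated 277. The other seven entries also reproduce. The completer numbers are 350 × 0.70 = 245 and 350 × 0.80 = 280.

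**Step 2: what the interaction estimates.** Let L be a person's Baseline device level, D the change to Month 12, and let the cognitive slope be a + b·L + c·D + error. The modification question is about c.

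- Quantiles at Baseline: the expected slope given L is a + b·L + c·E(D | L). If D is independent of L, c drops out and the test sees only b.
- Quantiles at Month 12 (L + D), or time-varying: b and c both enter, and the test cannot separate them.
- If modification acts through raw change, with equal SDs at both visits and correlation r between them, the correlation of D with L is −√((1 − r)/2). That is −0.50, −0.39 and −0.27 for r = 0.5, 0.7 and 0.85. The Baseline test then reacts to c, but with the opposite sign.

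**Step 3: simulation.** From the documents: n = 245 and 280, and 5% two-sided alpha. Assumed, because the documents give no values: r = 0.5, 0.7, 0.85; slope residual SD 1; effect 0.2 or 0.3 slope-SD per SD of the exposure. Quartile-by-time is a 3-df test of slopes, 2,000 runs per cell. The time-varying version is GLS on two visits, 1,500 runs, effect 0.3 only. Rejection rates at n = 245, ranges over r:

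| Truth | Effect | Baseline quartile | Month 12 quartile | Time-varying quartile | Change adjusted for Baseline |
|---|---|---|---|---|---|
| Nothing | 0 | 4–5% | 5–6% | 5–6% | 4–5% |
| Level only | 0.2 | 66–69% | 18–49% | not run | 4–5% |
| Level only | 0.3 | 95–97% | 38–86% | 81–94% | 5–6% |
| Modification only, independent of level | 0.2 | 5–6% | 23–53% | not run | 87% |
| Modification only, independent of level | 0.3 | 5% | 43–88% | 20–56% | over 99% |
| Modification through raw change | 0.2 | 9–20% | 10–19% | not run | 75–85% |
| Modification through raw change | 0.3 | 13–38% | 13–37% | not run | 98–99% |

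At n = 280 and r = 0.7, Baseline quartiles reject 73% and 98% for level only, and 5% for modification only.

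**Step 4: other inputs.** With n = 260, level SD 1, within-person change SD 0.6, residual SD 0.5 and effects of 0.15–0.20 (all assumed), modification alone gives 4–6% with Baseline quartiles, 11–18% with Month 12 quartiles and 6–9% with time-varying quartiles. A change term adjusted for Baseline gives 55–78%.

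**Step 5: why the Baseline value must be in the model.** Because D is negatively correlated with L, an unadjusted change term rejects 13–61% of the time at n = 245 when only level matters. Adjusted, it rejects 4–6%.

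**The case against.** The case on the other side has several parts.

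- A reader might infer that the planned test can never detect an effect of modification. The SAP does not support that, because it does not name the visit for the quantiles. With Month 12 or time-varying quantiles the test does respond, at 20–88% in the main settings. The statement is exact only if quantiles are cut at Baseline and change is independent of level. What stands is that the test cannot isolate modification under any reading.
- A reader might also infer that Aims B.iv and C.iv go unanswered. Aim B.iv asks for within-person change in activity and sleep, and the pre-post MMRM provides that. Aim C.iv, "Association between change in modifiable risk factors and change in cognition", is served for questionnaire-measured behaviour by SAP 8.4.4.5, and the questionnaires include physical activity and sleep. Only the device-based question is left open.
- A further inference would be that this test selects the Phase B interventions. Protocol 1.2 says only that outcome data from the programme will serve the Master Trial Protocol in general.
- No sentence ties the interaction to the modification clause. That is fair, but if they are not tied, the clause has no analysis at all.
- A change term is not causal either. In a run where a shared health change moved both activity (correlation about 0.45) and cognition (0.15–0.20 SD), with no effect of activity, the change term was significant 33–50% of the time. These inputs are also assumed. This objection stands, and it limits the wording of any result.

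**Conclusion.** The mismatch is real but limited. SAP 8.4.6 poses a question about modification, and nothing in the SAP relates device-measured change to change in cognition. The interaction it specifies responds to level under every reading of the quantile visit. If the quantiles are taken at Baseline and change is independent of level, rejection for a true modification effect stays at about 5%. With Month 12 or time-varying quantiles, power is weak to moderate in most settings and is always mixed with level.

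The percentages rest on assumed effect sizes, visit-to-visit correlations and residual SDs. The simulations use a person's slope or two visits rather than the full five-burst model, and take all completers as having recordings at both visits. The algebra in step 2 needs no effect size. The analysis is exploratory, so the primary result, Aim B.iv and the questionnaire part of Aim C.iv are unaffected. With one group and no control, even the corrected analysis shows an association, not an effect of modification. The change is worth making because it is cheap and closes a gap between question and test.

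**What to change.** 1. For each device measure, enter the Baseline value and the Month 12 minus Baseline change in the burst-score mixed model, each interacting with time, and use all five bursts. Take the baseline-adjusted change-by-time term as the result, and list the model's covariates.
2. Keep quantile-by-time only to describe who declines, and state which visit supplies the quantiles.
3. Reword the actigraphy sentence as the association of within-person change in activity or sleep with change in cognition. Reword the EEG sentence as within-person change following the programme.

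If the sponsor prefers to keep only the level-by-time test, the minimum is to name the visit and restate the question as an association with level.

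Cost: SAP wording and one re-specified exploratory model on data already being collected. The change term needs recordings at both visits, or imputed values, and shared changes in health can still confound it.

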Appendix 1: BHSP Consort Diagram
